APPENDIX 13: DIARY CARD

WRAIR

Walter Reed Army
Institute of Research

Soldier Health • World Health

RV 507 Participant Diary Card

Walter Reed Army Institute of Research
Clinical Trials Center

Version 1.7
13 February 2019

Participant ID

Walter Reed Army Institute of Research
Clinical Trials Center
[name]
[name] 20910
[contact]
After Work Hours: [contact]

Participant ID

Symptoms Severity Scale

None = you have no symptoms

Mild = minimal symptoms; cause minimal or no interference with work, school, or self care activities.

Moderate = notable symptoms; required modification in activity or medication; did not result in loss of work or cancellation of social activities

Severe = incapacitating symptoms; requiring bed rest and/or resulted in loss of work or cancellation of social activities.

**For any Problems Call:
[contact] OR [contact]**

Injection Site Pain Severity Scale

None = no pain

Mild = minimal pain; no limitation of use of arm.

[figure not shown]
[figure not shown]
[figure not shown]
Moderate = notable pain; some limitation of use of arm.

Severe = extreme pain; complete limitation of use of arm.

How to Measure Swelling and Redness at the Injection Site

1. Determine the widest part (or diameter) of the area.
2. Using the ruler that the clinic staff gave to you, measure the widest part of the area in centimeters (cm) as shown on the pictures below. Each small hash mark on the centimeter ruler equals one tenth (0.1) of a centimeter.
3. Measure the swelling (raised area) and the redness (red area) separately and record each measurement on the diary card.

Please complete this diary in black or blue ink only

Participant ID

Day of Vaccination

Date: ____/____/____ (dd/mmm/yyyy)

The evening of the day of Vaccination:

Temp: _____ (oral, °F) Time Taken: _____ PM

If you have a fever and wish to take your temperature again, record your additional temperature:

Temp: _____ (oral, °F) Time Taken: _____ AM / PM (circle)

Temp: _____ (oral, °F) Time Taken: _____ AM / PM (circle)

Are you taking any medication? Yes No

If yes, please list medication(s):

Please use the symptom scale at the bottom of the page

| Gen. Symptoms | None | Mild | Moderate | Severe |
|--------------------------------------|------|------|----------|--------|
| Joint Pain | | | | |
| Unusually Tired | | | | |
| Muscle Aches (not at injection site) | | | | |
| Headache | | | | |
| Chills | | | | |
| Nausea | | | | |

| Injection Site Symptoms | None | Mild | Moderate | Severe |
|---------------------------|--------------|------|---|--------|
| Local Pain | | | | |
| Swelling Measure in cm | ____.____ cm | | Please record in cm, the largest width measurement of the swelling (Example: 2.5 cm) | |
| Redness Measure in cm | ____.____ cm | | Please record in cm, the largest width measurement of the redness (Example: 2.5 cm) | |

Symptoms Severity Scale**None** = no symptoms**Mild** = minimal symptoms; cause minimal or no interference with work, school, or self-care activities.**Moderate** = notable symptoms; required modification in activity or medication; did not result in loss of work or cancellation of social activities.**Severe** = incapacitating symptoms; requiring bed rest and/or resulted in loss of work or cancellation of social activities.**For any problems call: [contact] OR [contact]****Injection Site Pain Severity Scale****None** = no pain**Mild** = minimal pain; no limitation of use of arm**Moderate** = notable pain; some limitation of use of arm**Severe** = extreme pain; complete limitation of use of arm

Participant ID

Day 1 after Vaccination

Date: ____/____/____ (dd/mmm/yyyy)

Temp: _____ (oral, °F) Time Taken: _____ AM / PM (circle)

If you have a fever and wish to take your temperature again, record your additional temperature:

Temp: _____ (oral, °F) Time Taken: _____ AM / PM (circle)

Temp: _____ (oral, °F) Time Taken: _____ AM / PM (circle)

Are you taking any medication? Yes No

If yes, please list medication(s):

Please use the symptom scale at the bottom of the page

| Gen. Symptoms | None | Mild | Moderate | Severe |
|--------------------------------------|------|------|----------|--------|
| Joint Pain | | | | |
| Unusually Tired | | | | |
| Muscle Aches (not at injection site) | | | | |
| Headache | | | | |
| Chills | | | | |
| Nausea | | | | |

| Injection Site Symptoms | None | Mild | Moderate | Severe |
|---------------------------|--------------|------|--|--------|
| Local Pain | | | | |
| Swelling Measure in cm | ____.____ cm | | Please record in cm, the largest width measurement of the swelling (Example: 2.5 cm) | |
| Redness Measure in cm | ____.____ cm | | Please record in cm, the largest width measurement of the redness (Example: 2.5 cm) | |

Symptoms Severity Scale**None** = no symptoms**Mild** = minimal symptoms; cause minimal or no interference with work, school, or self-care activities.**Moderate** = notable symptoms; required modification in activity or medication; did not result in loss of work or cancellation of social activities.**Severe** = incapacitating symptoms; requiring bed rest and/or resulted in loss of work or cancellation of social activities.**For any problems call: [contact] OR [contact]****Injection Site Pain Severity Scale****None** = no pain**Mild** = minimal pain; no limitation of use of arm**Moderate** = notable pain; some limitation of use of arm**Severe** = extreme pain; complete limitation of use of arm

Participant ID

Day 2 after Vaccination

Date: ____/____/____ (dd/mmm/yyyy)

Temp: _____ (oral, °F) Time Taken: _____ AM / PM (circle)

If you have a fever and wish to take your temperature again, record your additional temperature:

Temp: _____ (oral, °F) Time Taken: _____ AM / PM (circle)

Temp: _____ (oral, °F) Time Taken: _____ AM / PM (circle)

Are you taking any medication? Yes No

If yes, please list medication(s):

Please use the symptom scale at the bottom of the page

| Gen. Symptoms | None | Mild | Moderate | Severe |
|--------------------------------------|------|------|----------|--------|
| Joint Pain | | | | |
| Unusually Tired | | | | |
| Muscle Aches (not at injection site) | | | | |
| Headache | | | | |
| Chills | | | | |
| Nausea | | | | |

| Injection Site Symptoms | None | Mild | Moderate | Severe |
|-------------------------|--------------|------|---|--------|
| Local Pain | | | | |
| Swelling Measure in cm | ____.____ cm | | Please record in cm, the largest width measurement of the swelling (Example: 2.5 cm) | |
| Redness Measure in cm | ____.____ cm | | Please record in cm, the largest width measurement of the redness (Example: 2.5 cm) | |

Symptoms Severity Scale

None = no symptoms**Mild** = minimal symptoms; cause minimal or no interference with work, school, or self-care activities.**Moderate** = notable symptoms; required modification in activity or medication; did not result in loss of work or cancellation of social activities.**Severe** = incapacitating symptoms; requiring bed rest and/or resulted in loss of work or cancellation of social activities.

For any problems call: [contact] OR [contact]

Injection Site Pain Severity Scale

None = no pain**Mild** = minimal pain; no limitation of use of arm**Moderate** = notable pain; some limitation of use of arm**Severe** = extreme pain; complete limitation of use of arm

Participant ID

Day 3 after Vaccination

Date: ____/____/____ (dd/mmm/yyyy)

Temp: _____ (oral, °F) Time Taken: _____ AM / PM (circle)

If you have a fever and wish to take your temperature again, record your additional temperature:

Temp: _____ (oral, °F) Time Taken: _____ AM / PM (circle)

Temp: _____ (oral, °F) Time Taken: _____ AM / PM (circle)

Are you taking any medication? Yes No

If yes, please list medication(s):

Please use the symptom scale at the bottom of the page

| Gen. Symptoms | None | Mild | Moderate | Severe |
|--------------------------------------|------|------|----------|--------|
| Joint Pain | | | | |
| Unusually Tired | | | | |
| Muscle Aches (not at injection site) | | | | |
| Headache | | | | |
| Chills | | | | |
| Nausea | | | | |

| Injection Site Symptoms | None | Mild | Moderate | Severe |
|---------------------------|--------------|------|---|--------|
| Local Pain | | | | |
| Swelling Measure in cm | ____.____ cm | | Please record in cm, the largest width measurement of the swelling (Example: 2.5 cm) | |
| Redness Measure in cm | ____.____ cm | | Please record in cm, the largest width measurement of the redness (Example: 2.5 cm) | |

Symptoms Severity Scale

None = no symptoms**Mild** = minimal symptoms; cause minimal or no interference with work, school, or self-care activities.**Moderate** = notable symptoms; required modification in activity or medication; did not result in loss of work or cancellation of social activities.**Severe** = incapacitating symptoms; requiring bed rest and/or resulted in loss of work or cancellation of social activities.

For any problems call: [contact] OR [contact]

Injection Site Pain Severity Scale

None=no pain**Mild** = minimal pain; no limitation of use of arm**Moderate** = notable pain; some limitation of use of arm**Severe** = extreme pain; complete limitation of use of arm

Participant ID

Day 4 after Vaccination

Date: ____/____/____ (dd/mmm/yyyy)

Temp: _____ (oral, °F) Time Taken: _____ AM / PM (circle)

If you have a fever and wish to take your temperature again, record your additional temperature:

Temp: _____ (oral, °F) Time Taken: _____ AM / PM (circle)

Temp: _____ (oral, °F) Time Taken: _____ AM / PM (circle)

Are you taking any medication? Yes No

If yes, please list medication(s):

Please use the symptom scale at the bottom of the page

| Gen. Symptoms | None | Mild | Moderate | Severe |
|--------------------------------------|------|------|----------|--------|
| Joint Pain | | | | |
| Unusually Tired | | | | |
| Muscle Aches (not at injection site) | | | | |
| Headache | | | | |
| Chills | | | | |
| Nausea | | | | |

| Injection Site Symptoms | None | Mild | Moderate | Severe |
|---------------------------|--------------|------|---|--------|
| Local Pain | | | | |
| Swelling Measure in cm | ____.____ cm | | Please record in cm, the largest width measurement of the swelling (Example: 2.5 cm) | |
| Redness Measure in cm | ____.____ cm | | Please record in cm, the largest width measurement of the redness (Example: 2.5 cm) | |

Symptoms Severity Scale

None = no symptoms**Mild** = minimal symptoms; cause minimal or no interference with work, school, or self-care activities.**Moderate** = notable symptoms; required modification in activity or medication; did not result in loss of work or cancellation of social activities.**Severe** = incapacitating symptoms; requiring bed rest and/or resulted in loss of work or cancellation of social activities.

For any problems call: [contact] OR [contact]

Injection Site Pain Severity Scale

None = no pain**Mild** = minimal pain; no limitation of use of arm**Moderate** = notable pain; some limitation of use of arm**Severe** = extreme pain; complete limitation of use of arm

Participant ID

Day 5 after Vaccination

Date: ____/____/____ (dd/mmm/yyyy)

Temp: _____ (oral, °F) Time Taken: _____ AM / PM (circle)

If you have a fever and wish to take your temperature again, record your additional temperature:

Temp: _____ (oral, °F) Time Taken: _____ AM / PM (circle)

Temp: _____ (oral, °F) Time Taken: _____ AM / PM (circle)

Are you taking any medication? Yes No

If yes, please list medication(s):

Please use the symptom scale at the bottom of the page

| Gen. Symptoms | None | Mild | Moderate | Severe |
|--------------------------------------|------|------|----------|--------|
| Joint Pain | | | | |
| Unusually Tired | | | | |
| Muscle Aches (not at injection site) | | | | |
| Headache | | | | |
| Chills | | | | |
| Nausea | | | | |

| Injection Site Symptoms | None | Mild | Moderate | Severe |
|---------------------------|--------------|------|---|--------|
| Local Pain | | | | |
| Swelling Measure in cm | ____.____ cm | | Please record in cm, the largest width measurement of the swelling (Example: 2.5 cm) | |
| Redness Measure in cm | ____.____ cm | | Please record in cm, the largest width measurement of the redness (Example: 2.5 cm) | |

Symptoms Severity Scale

None = no symptoms**Mild** = minimal symptoms; cause minimal or no interference with work, school, or self-care activities.**Moderate** = notable symptoms; required modification in activity or medication; did not result in loss of work or cancellation of social activities.**Severe** = incapacitating symptoms; requiring bed rest and/or resulted in loss of work or cancellation of social activities.

For any problems call: [contact] OR [contact]

Injection Site Pain Severity Scale

None = no pain**Mild** = minimal pain; no limitation of use of arm**Moderate** = notable pain; some limitation of use of arm**Severe** = extreme pain; complete limitation of use of arm

Participant ID

Day 6 after Vaccination

Date: ____/____/____ (dd/mmm/yyyy)

Temp: _____ (oral, °F) Time Taken: _____ AM / PM (circle)

If you have a fever and wish to take your temperature again, record your additional temperature:

Temp: _____ (oral, °F) Time Taken: _____ AM / PM (circle)

Temp: _____ (oral, °F) Time Taken: _____ AM / PM (circle)

Are you taking any medication? Yes No

If yes, please list medication(s):

Please use the symptom scale at the bottom of the page

| Gen. Symptoms | None | Mild | Moderate | Severe |
|--------------------------------------|------|------|----------|--------|
| Joint Pain | | | | |
| Unusually Tired | | | | |
| Muscle Aches (not at injection site) | | | | |
| Headache | | | | |
| Chills | | | | |
| Nausea | | | | |

| Injection Site Symptoms | None | Mild | Moderate | Severe |
|---------------------------|--------------|------|--|--------|
| Local Pain | | | | |
| Swelling Measure in cm | ____.____ cm | | Please record in cm, the largest width measurement of the swelling (Example: 2.5 cm) | |
| Redness Measure in cm | ____.____ cm | | Please record in cm, the largest width measurement of the redness (Example: 2.5 cm) | |

Symptoms Severity Scale**None** = no symptoms**Mild** = minimal symptoms; cause minimal or no interference with work, school, or self-care activities.**Moderate** = notable symptoms; required modification in activity or medication; did not result in loss of work or cancellation of social activities.**Severe** = incapacitating symptoms; requiring bed rest and/or resulted in loss of work or cancellation of social activities.**For any problems call: [contact] OR [contact]****Injection Site Pain Severity Scale****None** = no pain**Mild** = minimal pain; no limitation of use of arm**Moderate** = notable pain; some limitation of use of arm**Severe** = extreme pain; complete limitation of use of arm

Participant ID

Day 7 after Vaccination

Date: ____/____/____ (dd/mmm/yyyy)

Temp: _____ (oral, °F) Time Taken: _____ AM / PM (circle)

If you have a fever and wish to take your temperature again, record your additional temperature:

Temp: _____ (oral, °F) Time Taken: _____ AM / PM (circle)

Temp: _____ (oral, °F) Time Taken: _____ AM / PM (circle)

Are you taking any medication? Yes No

If yes, please list medication(s):

Please use the symptom scale at the bottom of the page

| Gen. Symptoms | None | Mild | Moderate | Severe |
|--------------------------------------|------|------|----------|--------|
| Joint Pain | | | | |
| Unusually Tired | | | | |
| Muscle Aches (not at injection site) | | | | |
| Headache | | | | |
| Chills | | | | |
| Nausea | | | | |

| Injection Site Symptoms | None | Mild | Moderate | Severe |
|---------------------------|--------------|------|--|--------|
| Local Pain | | | | |
| Swelling Measure in cm | ____.____ cm | | Please record in cm, the largest width measurement of the swelling (Example: 2.5 cm) | |
| Redness Measure in cm | ____.____ cm | | Please record in cm, the largest width measurement of the redness (Example: 2.5 cm) | |

Symptoms Severity Scale**None** = no symptoms**Mild** = minimal symptoms; cause minimal or no interference with work, school, or self-care activities.**Moderate** = notable symptoms; required modification in activity or medication; did not result in loss of work or cancellation of social activities.**Severe** = incapacitating symptoms; requiring bed rest and/or resulted in loss of work or cancellation of social activities.**For any problems call: [contact] OR [contact]****Injection Site Pain Severity Scale****None** = no pain**Mild** = minimal pain; no limitation of use of arm**Moderate** = notable pain; some limitation of use of arm**Severe** = extreme pain; complete limitation of use of arm

Participant ID

If you have any of the General or Injection Site Symptoms that is still ongoing after day 7, please complete stop dates below.

| General Symptoms | Date the Symptom Ended | Maximum severity after day 7 (Mild, moderate or severe) |
|---|-------------------------------|--|
| Joint Pain | | |
| Unusually Tired | | |
| Muscle Aches (not at injection site) | | |
| Headache | | |
| Chills | | |
| Nausea | | |

| Injection Site Symptoms | Date the Symptom Ended | Maximum severity after day 7 (Mild, moderate or severe) |
|--------------------------------|-------------------------------|--|
| Local pain | | |
| Swelling Measure in cm | | ____. cm |
| Redness Measure in cm | | ____. cm |

Are you or have you taken any medication after day 7? If so, please record the name of the medication and the date you stopped taking the medication below, if applicable.

| Name of Medication | Date You Stopped Medication |
|---------------------------|------------------------------------|
| | |
| | |
| | |
| | |
| | |

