5.2. Administration of the Study Injection

Injections will be administered IM in a 1 mL volume by needle and syringe. It is recommended, but not required, that the injection be administered into the non-dominant arm. When choosing an arm for the injection, clinicians should consider if there is an arm injury, local skin problem or significant tattoo that precludes administering the injection or will interfere with evaluating the arm after injection. Procedures for follow-up in the clinic after vaccination are shown in Appendix 1.

Following the study injection, participants will be observed in the WRAIR CTC for a minimum of 30 or 60 minutes (60 minutes for first 3 participants of each group and a minimum of 30 minutes for subsequent participants in each group). Vital signs (temperature, blood pressure, and pulse) will be taken 30 or 60 minutes post-injection. The injection site will be inspected for evidence of local reaction during this period. In keeping with good medical practice, acute medical care will be provided to participants for any immediate allergic reactions or other injury resulting from participation in this research study.

In the event of a severe allergic reaction, the CTC is staffed with trained medical personnel and stocked with appropriate medical emergency equipment to provide acute care for conditions such as anaphylaxis. Further, if required, a formal emergency medical response service (fire department), capable of treating and transferring any life-threatening injuries to a higher level of medical care, is available in close proximity to the trial site.

5.2.1. 7-Day Solicited Reactogenicity and Follow-up

Temperature and solicited local and systemic signs/symptoms will be recorded in the clinic prior to vaccination and at a minimum of 30 minutes post injection and then daily by the participant for 7 days. Solicited symptoms that persist after the end of day 7 will be considered an AE/SAE and will be reported (see section 7.5) and followed through resolution.

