Participants will be given a “Diary Card”, a thermometer, and a ruler. The diary card will be used as a memory aid, on which the participant will record temperature, local and systemic symptoms and concomitant medications daily for 7 days after the injection. Participants will be trained to complete the paper diary card, how to use the thermometer, and how to measure injection site swelling and redness using the ruler. Completion of the diary card training will be noted in source documents. The written (paper) diary card will be transcribed into the study database and will be stored in the participant file for monitoring purposes.

The solicited signs and symptoms on the diary card (among others) will include: joint pain, unusually tired, muscles aches (other than at injection site), headache, chills, nausea, and pain at injection site. Participants will also record the day’s highest measured temperature and measurement of largest diameter for redness and swelling at the injection site. The completed diary cards are collected at the first visit following completion of the 7-day diary card (about 2 weeks after the injection).

Follow-up on participant well-being will be performed by telephone or clinic visit on the day following vaccination and by clinic visit on Day 3 following the injection to assess their clinical status. Participants may call or come to the clinic at any time-point for evaluation, if they experience unusual, moderate or severe signs and symptoms. Diary cards will be reviewed with the clinician at any visit from day of vaccination through the first study visit following completion of the diary card. If upon reviewing the clinician finds that general symptom or injection site symptom information (except swelling or redness measurements) is missing from the diary cards, the participant will be asked to provide the missing information to the best of their recollection.

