7.0 PHARMACOVIGILANCE, SAFETY AND ADVERSE EVENT REPORTING

7.1. Definitions

Adverse Events

An adverse event (AE) is any untoward or unfavorable medical occurrence in a participant administered a pharmaceutical product and does not necessarily have a causal relationship with this product. An AE can therefore be any unfavorable and unintended sign (including an abnormal laboratory finding), symptom, or disease temporally associated with the use of a study product, whether or not considered related to the study product. (International Conference on Harmonization (ICH) E6) (Synonym: Adverse Experience).

Serious Adverse Events

As defined in 21 CFR 312.32, an adverse event or suspected adverse reaction is considered "serious" if, in the view of either the investigator or sponsor, it results in any of the following outcomes: "Death, a life-threatening adverse event, inpatient hospitalization or prolongation of existing hospitalization, a persistent or significant incapacity or substantial disruption of the ability to conduct normal life functions, or a congenital anomaly/birth defect. Important medical events that may not result in death, be life-threatening, or require hospitalization may be considered serious when, based upon appropriate medical judgment, they may jeopardize the participant and may require medical or surgical intervention to prevent one of the outcomes listed in this definition. Examples of such medical events include allergic bronchospasm requiring intensive treatment in an emergency room or at home, blood dyscrasias or convulsions that do not result in inpatient hospitalization, or the development of drug dependency or drug abuse."

"Life-threatening" refers to an adverse event that at occurrence represents an immediate risk of death to the participant; it does not refer to an event that hypothetically might have caused death if it were more severe. Similarly, a hospital admission for an elective procedure is not considered an SAE.

All AEs will have their possible relationship to study vaccine assessed and will be graded according to the table for grading severity of adverse events (see Appendix 9). Arthralgia (joint pain) and arthritis AEs will be graded in accordance with the criteria in Appendix 10.

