[figure not shown]
**APPENDIX 10: DAIDS TABLE FOR GRADING SEVERITY OF ARTHRALGIA
ADVERSE EVENTS**

[figure not shown]
The following excerpt from the DAIDS AE Grading Table Corrected (Version 2.1-July 2017) will be used to grade reported events of joint pain (arthralgia). Solicited AEs involving arthralgias will be graded using the arthralgia criteria whereas unsolicited AEs involving arthralgias will be graded using the appropriate row based on the presence of symptoms.

| PARAMETER | GRADE 1 MILD | GRADE 2 MODERATE | GRADE 3 SEVERE | GRADE 4 POTENTIALLY LIFE- THREATENING |
|---|--|---|---|--|
| Arthralgia | Joint pain causing no or minimal interference with usual social & functional activities | Joint pain causing greater than minimal interference with usual social & functional activities | Joint pain causing inability to perform usual social & functional activities | Disabling joint pain causing inability to perform basic self-care functions |
| Arthritis (objective findings on PE corresponding to the joint pain) | Stiffness or joint swelling causing no or minimal interference with usual social & functional activities | Stiffness or joint swelling causing greater than minimal interference with usual social & functional activities | Stiffness or joint swelling causing inability to perform usual social & functional activities | Disabling joint stiffness or swelling causing inability to perform basic self-care functions |

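### The diary card rates severity by definitions that differ from Appendix 9 and omits swelling function, and Section 8.3.2 does not say which severity the reactogenicity table uses

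*Combined protocol and SAP*

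**What the plan says.** **Governing scale.** Section 7.1 says that all adverse events "will be graded according to the table for grading severity of adverse events (see Appendix 9"), with joint pain and arthritis graded by Appendix 10. That this covers solicited events is clear from Appendix 10: "Solicited AEs involving arthralgias will be graded using the arthralgia criteria". Appendix 9 has its own rows for injection-site pain, swelling, redness, nausea, headache, fatigue and myalgia, and a default rule for anything without a row.

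**Card scale.** For general symptoms the Appendix 13 card gives "Mild = minimal symptoms; cause minimal or no interference with work, school, or self care activities" and "Moderate = notable symptoms; required modification in activity or medication; did not result in loss of work or cancellation of social activities". Severe means bed rest, lost work or cancelled social activities. Injection-site pain has a separate scale based only on how far use of the arm is limited. Swelling and redness are entered in cm.

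**From card to database.** Section 5.2.1 says "The diary card will be used as a memory aid", provides for review with a clinician, and then says "The written (paper) diary card will be transcribed into the study database and will be stored in the participant file for monitoring purposes". Section 7.2 gives severity determinations to the clinical investigators and mentions a post-injection reactogenicity (PIR) case report form, which is not in these documents.

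**After day 7.** The last page of the card asks for "Maximum severity after day 7 (Mild, moderate or severe"). Section 5.2.1 says of the same symptoms: "Solicited symptoms that persist after the end of day 7 will be considered an AE/SAE and will be reported".

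**Analysis.** Section 8.3.2 tabulates each reactogenicity sign or symptom by group and severity, counting a participant once at maximum severity. It does not name the severity scale.

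**The concern.** Two sets of severity definitions apply to the same symptoms. One is written down daily by the participant and transcribed; the other is named as the grading standard. No passage says how an entry on the first becomes a grade on the second, or which of them the Section 8.3.2 table reports. Where the definitions disagree, a participant's row in that table depends on a choice the plan leaves open. For swelling the problem goes further: the card does not collect one of the two elements that Appendix 9 needs. At stake is the severity description of reactogenicity, by dose group and overall, which is the main descriptive safety output of a dose-escalation study with 20 participants per group.

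**Working it through.** No sample size, power or interval in the plan rests on this point, so there is no figure to reproduce. The check is a row-by-row comparison.

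**Items on the card.** Six general symptoms + three injection-site items = 9. Rated Mild/Moderate/Severe: 6 general + local pain = 7. Measured in cm: swelling and redness = 2.

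| Card item | Card scale | Appendix 9 or 10 | Result |
|---|---|---|---|
| Headache | No narcotic criterion; Severe needs bed rest, lost work or cancelled activities | Grade 3 on any narcotic use, or if daily activity is prevented | Clear difference: narcotic taken, no bed rest, no lost work or cancelled activity = card Moderate, Grade 3 |
| Local pain | Limitation of arm use only | Grade 3 on any narcotic use, or if daily activity is prevented | Clear difference: some arm limitation plus a narcotic = card Moderate, Grade 3 |
| Chills | Severe on bed rest alone | No own row; default Grade 3 needs daily activity prevented and medical intervention | Clear difference: bed rest without medical intervention = card Severe, Grade 3 not met |
| Fatigue, myalgia | Mild allows minimal interference | Grade 1 is no interference, Grade 2 some interference | Small: turns on minimal versus none |
| Nausea | Severe on lost work | Grade 3 names prevented activity and outpatient IV hydration, joined by a comma | Depends on whether the comma means and or or |
| Joint pain | Mild is minimal or no interference | Appendix 10 Grade 1 is no or minimal interference | Close |

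So, of the seven rated items, three differ clearly (headache, local pain, chills), three differ slightly or depending on reading (fatigue, myalgia, nausea), and one matches closely (joint pain).

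**Swelling.** Appendix 9 Grade 1 is 2.5–5 cm without interference. Grade 3 is more than 10 cm or daily activity prevented. Footnote 2 to that table asks for grading on function as well as size. The card asks for the width only. A 3 cm swelling that prevents daily activity is therefore Grade 3, but the card entry (3.0 cm) falls in the 2.5–5 cm band and supports only Grade 1. Redness is graded on size up to Grade 3, so its cm entry is sufficient there.

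**What the card can supply.** Each daily page asks for medications taken by name, so a narcotic may be visible to the reviewer. The page does not ask for the reason or the number of doses. The only review task that Section 5.2.1 spells out is recovering missing entries. It does not mention re-rating a completed one, or asking about swelling and activity.

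**After day 7.** A persisting symptom is an adverse event and is graded by Appendix 9 under Section 7.1, while the card still collects a Mild/Moderate/Severe rating for it. One symptom can then carry both ratings.

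**Weight of one participant in the table.** 1/20 = 5 percentage points in a dose group; 1/40 = 2.5 percentage points overall. The documents give no basis for how many participants would change row, and none is assumed.

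**The case against.** The strongest reply is that the scale and the grader are already named. Section 7.1 and Appendix 10 point to the grading tables, Section 7.2 has investigators determine severity, and the card is only a memory aid reviewed with a clinician. A clinician who grades from the history needs no conversion rule. The medication list carries much of the analgesic information, and swelling function can be asked about at the Day 3 and Day 7 visits. The PIR form may already record the Appendix 9/10 grade. On this view Section 8.3.2 lacks only a cross-reference.

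Much of that stands, and it limits the point. It does not remove it. Nothing in these documents requires the clinician to re-rate completed entries or to ask about swelling function, the card ratings themselves are transcribed, and Section 8.3.2 does not choose between the two severities.

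A reader might also infer more than the documents support:

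- That the card shifts severity in a known direction. The clear cases run both ways (card lower for narcotic-treated headache and local pain, higher for chills), and constructed cases say nothing about frequency.
- That six of the seven rated items are equally in conflict. Fatigue and myalgia turn on one word and nausea on a comma. A single non-narcotic dose for headache without interference fits card Mild as well as card Moderate.
- That the Section 7.4 pause rule could be triggered or missed on card ratings. That rule needs an event assessed as related, the Principal Investigator determines severity, and Section 7.2 records solicited events without attribution. A card entry alone cannot meet it.

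**Conclusion.** The concern holds in limited form. The governing scale is defined, but the transcribed card uses different definitions, clearly so for headache, local pain and chills. It cannot support the functional part of the swelling grade. Section 8.3.2 does not say which severity it tabulates. The effect is confined to the severity rows of the reactogenicity table, at 5 percentage points per participant moved within a dose group. The number moved is unknown. The primary endpoint in Section 3.1 is the occurrence of solicited signs and symptoms and does not depend on the scale.

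The conclusion assumes that no form outside these documents already makes the conversion. If the PIR form does, what remains is a missing cross-reference and the swelling item. The point should be corrected because the remedy is cheap. It does not threaten the study's main safety conclusion.

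**What to change.** 1. Add one card item on whether swelling interfered with activity or prevented it.
2. Have the investigator assign the Appendix 9/10 grade on the PIR form at diary review, or reconcile the card wording with those appendices. Either route uses tables the protocol already names and introduces no new clinical rule.
3. State in Sections 5.2.1 and 8.3.2 that the reactogenicity table uses that grade.

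If the PIR form already converts the entries, item 1 and a cross-reference in those two sections are enough.

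The cost is a revised card or form needing IRB approval, and a few sentences of protocol text. If enrolment has started, changing the card may leave two card versions in the data; grading on the PIR form keeps that to the added swelling item. No extra visits or participants are needed.
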